**Computed Tomography Coronary Angiography (CTCA) prior to Chronic Total Occlusion (CTO)
Percutaneous Coronary Intervention (PCI) - a feasibility study**

TRIAL SUMMARY

Trial Title	Computed Tomography Coronary Angiography (CTCA) prior to Chronic Total Occlusion (CTO) Percutaneous Coronary Intervention (PCI) - a feasibility study
Summary of Trial design	Randomised, prospective, single centre feasibility study of CTCA prior to CTO PCI
Site and Chief Investigator	Sandwell and West Birmingham NHS Trust, Birmingham, United Kingdom [name]
Participant population	Patients undergoing CTO PCI
Planned sample size	20
Number of sites	1
Intervention duration	Prior to index CTO PCI procedure
Follow up duration	6 months
Planned trial duration	1 year
Primary objective	To determine if CTCA prior to CTO PCI results in improved procedural success rate?
Secondary objectives	i) To determine if CTCA prior to CTO PCI results in improved angina as determined by Seattle Angina Questionnaire (SAQ)? ii) To determine if CTCA prior to CTO PCI reduces the need for a second procedure due to improved procedural success rate? iii) Are there procedural differences between the intervention arm (CTCA) and usual care
Intervention	Randomised to CTCA versus no CTCA prior to CTO PCI

ABBREVIATIONS:

CABG: Coronary Artery Bypass Graft

CAD: Coronary Artery Disease

CTCA: Computed Tomography Coronary Angiogram

CTO: Chronic Total Occlusion

J-CTO: Japanese Chronic Total Occlusion

PCI: Percutaneous Coronary Intervention

QALYS: Quality Adjusted Life Years

QoL: Quality of Life

SAQ: Seattle Angina Questionnaire

Trial Protocol Synopsis

Item	Description

Title
	
Computed Tomography Coronary Angiography (CTCA) prior to Chronic Total Occlusion (CTO) Percutaneous Coronary Intervention (PCI)

Introduction
	

Description of research question
	
Null Hypothesis: CTCA performed prior to CTO PCI will not improve procedural success
 
Existing knowledge: A chronic total occlusion (CTO) is present in 15-20% of patients with angina who are referred for coronary angiography. Due to the complexity of occlusive coronary artery disease (CAD), including a high prevalence of calcium and tortuosity within long segments of disease, CTO PCI is associated with higher procedural complication rates (11). Inability to detect the intraluminal path in the CTO artery, combined with calcification and tortuosity can result in unsuccessful guidewire crossing and procedural failure. Successful CTO PCI has been shown to improve Quality of Life (QoL) at 12 months(4). These patients are more likely to be angina free at 12 months (5, 6) as assessed by the Seattle Angina Questionnaire (SAQ) (7, 8). CTO PCI in symptomatic patients is cost effective and results in greater quality-adjusted-life-years (QALYS)(9, 10).
 
CTO percutaneous coronary intervention (PCI) procedure success rates increased from 68% to 79% between 2000 and 2011, and are as high as 90% when performed by high-volume CTO operators (2, 3). Complexity of the CTO is determined by several factors and several CTO complexity scores, derived from (invasive) angiographic lesion and clinical characteristics, have been shown to correlate with procedural success and complication rates (JCTO(12), PROGRESS(13), RECHARGE(14), Euro-CASTLE(15)). The most commonly utilised score is the J-CTO (Multicenter Chronic Total Occlusion Registry of Japan)(12) which assigns a score of 1 each to the angiographic CTO proximal cap (tapered or blunt), calcification, tortuosity (>45°), lesion length (≥20mm) and previous failure, with a maximum score =5. Scores ≥2 are considered CTOs that are difficult to perform and require advanced techniques for successful revascularisation.
 
In a proportion of these patients, the first procedure either fails completely or partially succeeds in forming a tract within the occluded artery but this is inadequate for stent delivery and the patient requires a second procedure, occasionally a third for complete success and

	
reconstruction of the fully occluded artery.
 
Angiographically, the CTO artery usually shows a short proximal portion of dye filled artery prior to the occlusion. In most patients there are some collaterals from the contralateral coronary artery which try to fill part of the occluded CTO artery. However the actual body of the CTO is not visible angiographically.
 
Computed Tomography Coronary Angiography (CTCA) can delineate the coronary anatomy in 3-dimensions, determining atherosclerotic plaque and occlusion location, severity and morphology. This makes it an attractive modality to assess the coronary CTO. Development of a CTCA based complexity score for stratifying CTOs by difficulty resulted in the CT-RECTOR score (Computed Tomography Registry of Chronic Total Occlusion Revascularization, table 1)(16). Variables included in this score are multiple occlusions, blunt stump, severe calcification, bending, duration of CTO ≥ 12 months and previously failed PCI (all scored 1). The CT-RECTOR score correlates with the J-CTO score and has a better area under ROC curve (ROC AUC 0.83 for CT-RECTOR score and 0.71 for J-CTO, $p < 0.001$) and predicts CTO PCI success (16)
 
The role of routine CTCA pre-CTO PCI is as yet undefined as current practice involves the use of CTCA in patients who have had an unsuccessful CTO PCI attempt or previous coronary artery bypass grafting (CABG).
 
Need for a feasibility study:
 
Current practice at our centre involves the use of CTCA in patients who have had an unsuccessful CTO PCI attempt or previous coronary artery bypass grafting (CABG) but the role of routine CTCA pre-CTO PCI is as yet undefined.
 
The small additional investment of a CTCA could help plan/improve a complex procedure and may reduce the need for additional procedures and readmissions.
 
The mean acute treatment cost of a CTO PCI is approximately (combined day-case –ordinary elective spell) £6933 (9, 17) whereas the approximate cost of a CTCA is £360 (as per local billing). Elective readmission for a failed CTO PCI procedure would entail an additional financial (to the provider) and emotional cost (to the patient).
 
The cost of an additional CTO PCI procedure aside, readmission and bed charges themselves can reach £1000/day (readmission =£255/day)(17)and bed

--	---

	
cost=£600/day). Including the cost of a second CTO PCI procedure (combined day-case –ordinary elective spell) £6933 (9, 17), the overall cost can total to £10,000. In contrast, the cost of a CTCA is £360 (as per local billing). Financial costs are one part of the issue, but a second CTO PCI procedure can also heighten patient anxiety and discomfort which are well known in patients prior to any PCI.
 
A feasibility study will help establish the role of a CTCA prior to CTO PCI to positively influence strategy and/or outcomes.

Objectives	
Primary:
 
i) Does performing a CTCA prior to CTO PCI improve the success of the CTO procedure?
 
Secondary:
 
i) To determine if CTCA prior to CTO PCI results in improved angina as determined using the Seattle Angina Questionnaire (SAQ) by SAQ.
 
ii) To determine if CTCA prior to CTO PCI reduces the need for a second procedure (due to improved procedural success rate).
 
iii) To assess if there are procedural differences between the intervention arm (CTCA) and usual care arm

Comparators	CTCA versus no CTCA prior to CTO PCI
Trial design	Randomised (1:1), prospective, single centre study
Methods (see figure 1)	
Study setting	Sandwell and West Birmingham NHS Trust, Birmingham, United Kingdom
Eligibility Criteria	
Inclusion Criteria:
 
Patients meeting all the below criteria will be included
 
 • ≥18 years • CTO with J-CTO score≥2 • Appropriate indication for CTO PCI • Adequate CTCA images for analysis 
Exclusion criteria:
 
Patients meeting any of the following criteria will be excluded
 
 • <18 years of age • CTO with J-CTO score<2 • Inadequate/degraded CTCA images • Pregnant/lactating women • Patients with severe contrast allergy • Patients unable to provide written informed consent

Intervention	
Experimental group: CTCA prior to CTO PCI Conventional group: CTO PCI
 
Patients will be randomised to CTCA or no CTCA prior to CTO PCI (figure 1)

Outcomes	
Outcomes
 
Primary endpoint
 
 i. CTO PCI success rate in CTCA arm versus no CTCA arm 
Secondary endpoints
 
 i. Angina by the SAQ summary score at 6 months ii. Compare the number of patients who required a second CTO PCI procedure in the CTCA arm versus no CTCA arm iii. Procedural differences between the intervention CTCA arm versus no CTCA arm including: 
 a) Health Economics: 
 • Cost saved per patient due to improved success and reduction in readmission or further procedure b) CTO PCI efficiency: 
 • Wire crossing time • Procedure time c) CTO PCI safety outcomes: 
 • Procedural complications (Ellis perforation, tamponade, acute kidney injury/contrast induced nephropathy, access site bleeding, donor vessel injury) • Radiation: CTCA dose, CTO PCI dose, and combined CTCA and CTO PCI dose • Contrast: CTCA volume, CTO PCI volume, and combined CTCA and CTO PCI volume d) Change in CTO PCI strategy hierarchy as a result of the CTCA review
Participant/project timeline	Please see figure 2
Sample size	This is a feasibility study- to ensure completion within a year, we have estimated 20 patients, randomised 1:1 to each arm (10 patients per arm) as a sample size in a moderate size hospital which performs approximately 100 CTO PCIs annually
Intervention assignment	Block randomisation with sealed envelope technique
Data collection, management and analysis	
 • eCRF and online database to collect demographic, procedural and SAQ information

	
 • SAQ summary score at 6 months post PCI • Blood samples pre and post PCI • Comparison of demographics, procedural details, procedural success and complications, bloods, SAQ, and financial cost between the CTCA and non-CTCA groups • Categorical variables will be presented as percentage and compared with the chi square or Fisher's test • Continuous variables will be presented as median (range) and compared with student's t-test or Mann Whitney test. • In addition, modelling will be performed by binary logistic regression analysis to predictors of CTO PCI success.
Monitoring	CTO PCI procedural adverse events will be reported as usual on the national database and this data will be collected in the eCRF.

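### Adequate CTCA images are an entry condition for every patient, although CTCA is the randomised intervention; with no as-allocated rule, this permits exclusions after randomisation from one arm only

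*Combined protocol and SAP*

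**What the plan says.** In the Trial Protocol Synopsis, Eligibility Criteria, the inclusion list opens with "Patients meeting all the below criteria will be included" and contains "Adequate CTCA images for analysis". The exclusion list opens with "Patients meeting any of the following criteria will be excluded" and contains "Inadequate/degraded CTCA images". Neither image criterion is limited to an arm.

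The Trial Summary gives the intervention as "Randomised to CTCA versus no CTCA prior to CTO PCI". The Synopsis row on Intervention agrees, and describes the conventional group as CTO PCI alone.

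The primary endpoint (Outcomes) is "CTO PCI success rate in CTCA arm versus no CTCA arm", with 10 patients planned per arm. The row on data collection and analysis compares the CTCA and non-CTCA groups. It defines no analysis set, has no as-allocated rule, and does not say what happens to a patient whose scan cannot be read.

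**The concern.** There are two linked problems.

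- **The eligibility rule conflicts with the design.** A patient allocated to no CTCA who has no earlier scan cannot satisfy a criterion that asks for adequate CTCA images.
- **The rule can act after randomisation, in one arm.** If the scan is done because of the allocation, its quality is discovered only in the CTCA arm. An investigator who then removes a patient with a degraded scan is following the written criteria, and nothing corresponds to this for an unscanned control. The primary comparison would then set a selected CTCA arm against an unselected control arm.

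The second problem bears on the trial's stated primary objective, whether CTCA improves procedural success. With 10 patients per arm, each exclusion shifts the result visibly.

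**Working it through.** **1. Who is scanned?** The text gives mixed signals.

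- *For scanning everyone:* the Appendix costing has £7,200 for CTCA at £360 each, and 7,200/360 = 20 scans. Ten CTCA-arm patients would need 10 × £360 = £3,600. The table is headed approximate. Its blood-test row also multiplies by 20 (£60 × 20 = £1,200), so this may be simple budgeting.
- *For scanning one arm:* the arms are named CTCA and no CTCA. CTCA radiation dose and contrast volume are listed under "Procedural differences between the intervention CTCA arm versus no CTCA arm including"; they would not be expected to differ if everyone were scanned.
- *Earlier scans:* the section on the need for a feasibility study says the centre already uses CTCA after a failed attempt or bypass surgery. Some controls may therefore hold images, but this cannot be assumed for all.

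Figure 1 (patient flow) is not in the text available for this review.

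**2. Size of the bias if unreadable scans are excluded from the CTCA arm.** The plan has no figure of its own to reproduce here. Let

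- u = share of CTCA-arm scans that are unreadable (assumed 10–30%);
- p = overall success. The values 68%, 79% and 90% come from the Synopsis background. They are general CTO PCI rates, whereas this trial enrols only J-CTO ≥2, which the same section calls difficult;
- g = success with readable scans minus success with unreadable scans (assumed 0–40 points);
- no true effect of CTCA.

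Success among retained CTCA patients is p + u·g, so the spurious difference is u·g:

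- g = 0: 0 points
- g = 20: 2 to 6 points (u = 10% to 30%)
- g = 40: 4 to 12 points. At p = 90%, u = 30%, readable success would be 0.90 + 0.12 = 1.02, which is impossible, so the bias is capped at 10.

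A larger gap gives more. If unreadable cases succeed 40% of the time against 79% overall, with u = 30%, retained success is (0.79 − 0.3 × 0.40)/0.7 = 95.7%, a bias of +16.7 points (a gap of about 56).

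**3. Arithmetic limits with g left free.** Upper limit = min(1 − p, p·u/(1 − u)); lower limit = −u(1 − p)/(1 − u). In points:

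| p | u = 10% | u = 20% | u = 30% |
|---|---|---|---|
| 68% | −3.6 to +7.6 | −8.0 to +17.0 | −13.7 to +29.1 |
| 79% | −2.3 to +8.8 | −5.2 to +19.8 | −9.0 to +21.0 |
| 90% | −1.1 to +10.0 | −2.5 to +10.0 | −4.3 to +10.0 |

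**4. How often it would arise with 10 CTCA patients.** If every unreadable scan led to exclusion, the number excluded is Binomial(10, u):

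| | u = 10% | u = 20% | u = 30% |
|---|---|---|---|
| At least one, 1 − (1 − u)^10 | 65% | 89% | 97% |
| At least two | 26% | 62% | 85% |
| Expected to remain | 9 | 8 | 7 |

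**5. Effect on an observed 8/10 (80%).**

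- One exclusion: 8/9 = 88.9% (+8.9 points) if it is a failure, 7/9 = 77.8% (−2.2) if a success.
- Two exclusions: 8/8 = 100% (+20), 7/8 = 87.5% (+7.5) or 6/8 = 75% (−5).

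**The case against.** The best defence is that the plan is read too literally. Figure 1 may show who is scanned and when. The inclusion item may mean adequate images where a scan is done, or may concern only the CTCA review behind the strategy-change endpoint. A patient with no scan does not trigger the exclusion item. No sentence says that randomised patients will be removed, and an endpoint defined by arm reads naturally as the allocated groups. Finally, at 79% success the 95% half-width for 10 against 10 is 1.96 × √(2 × 0.79 × 0.21/10), about 36 points, so an assumed bias of 0–12 points lies well within sampling error.

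Part of this stands. The exclusion is permitted, not planned. Its rate and direction are assumptions: the background links calcification and tortuosity to procedural failure, but not to image quality. Figure 1 could settle the timing.

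The rest does not rescue the text. Reading the item as applying where a scan is done leaves the one-arm exclusion open. Scanning everyone before randomisation removes the one-arm route but contradicts the no-CTCA arm. If the item concerns only the image review, it does not belong in eligibility, yet it appears there twice. Wide sampling error does not excuse an avoidable bias in the primary comparison.

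**Conclusion.** The concern holds and must be fixed. The contradiction between an image requirement on all patients and an arm without CTCA is clear in the text, and confidence in it is high. Confidence in the bias route is moderate: it depends on the scan following allocation and on the criterion then being enforced.

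If both happen, the primary comparison is no longer between the groups as randomised. Under the assumed ranges (10–30% unreadable, gap 0–40 points, no true effect), the spurious benefit is 0–12 points. It is zero if readability is unrelated to success, and works against CTCA if unreadable scans are commoner in easier lesions.

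**What to change.** 1. State who is scanned and when, in the text and consistently with Figure 1.
2. Restrict eligibility to features that can be assessed before randomisation in both arms:
   - if only the CTCA arm is scanned, remove both image-quality criteria from eligibility;
   - if everyone is scanned before randomisation, say so. Image adequacy is then a legitimate baseline criterion, but the description of the no-CTCA arm must be revised.
3. Reconcile the 20 scans in the costing with whichever applies.
4. State that every randomised patient is analysed for the primary endpoint in the allocated arm, including any CTCA-arm patient whose scan is missing or unreadable.
5. Label any analysis limited to readable scans, including that of the strategy-change endpoint, as secondary and non-randomised.
6. Optionally, report the number of non-diagnostic scans. Image quality is not named among the eCRF items, so this may need one added field.

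The cost of items 1–5 is amendment wording, with no extra patients, scans or visits. The statistical price is dilution: if CTCA helps only when the scan is readable, the estimated effect is the true effect × (1 − u). That retains 90% to 70% of it at the assumed rates, as would happen in routine use.

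### The health-economic endpoint is worded as a saving without naming the CTCA cost, so taken literally it is gross, not net; and a median cost would not register 0 to 4 repeats in an arm of 10

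*Combined protocol and SAP*

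**What the plan says.** In the combined protocol and SAP, the Outcomes section gives one health-economic endpoint, secondary endpoint iii a: "Cost saved per patient due to improved success and reduction in readmission or further procedure". Endpoint ii is separate: "Compare the number of patients who required a second CTO PCI procedure" in each arm.

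The section on data collection, management and analysis adds a between-group comparison of several items "and financial cost between the CTCA and non-CTCA groups". It does not say which costs enter. It has one rule for all continuous variables: "Continuous variables will be presented as median (range) and compared with student's t-test or Mann Whitney test". No rule is specific to cost.

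The rationale (Need for a feasibility study) prices a CTCA at £360 and a CTO PCI at £6,933, and says that with a second procedure "the overall cost can total to £10,000". The Existing knowledge section says of some patients whose first attempt fails or only partly succeeds that "the patient requires a second procedure, occasionally a third for complete success". The Sample size section gives 10 patients per arm, and the Trial Summary gives 6 months of follow-up.

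**The concern.** The rationale poses a trade-off: does a modest outlay on a scan repay itself by avoiding expensive repeats? The endpoint carries only the benefit side. The same list of endpoints shows how the other side could be written: radiation and contrast are each reported for the CTCA, for the PCI and for the two combined. Cost has no such line. Two analysts with the same data could therefore report figures up to about £360 per CTCA-arm patient apart, and with equal repeats one would report no difference where the other reports a net cost.

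The second issue is the summary statistic. Repeats are costly events in a minority of patients. A median is insensitive to such events, and the only stated summary for continuous variables is the median with the range. A reader could then see CTCA as dearer when its average cost is lower, which is the quantity a provider would budget on.

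**Working it through.** **Inputs.** CTCA £360, CTO PCI (index or repeat) £6,933 and repeat episode up to about £10,000, all from Need for a feasibility study; 10 per arm, from Sample size. Assumptions: one CTCA per CTCA-arm patient, and flat unit prices unless stated.

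**The plan's repeat cost.** The document does not state the number of days behind £10,000. Three days at its upper figure of £1,000 per day give 6,933 + 3 x 1,000 = £9,933, which is close. Three days at the itemised charges (255 + 600 = £855) give £9,498. Both £6,933 and £10,000 are carried below.

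**Gross against net.** Gross saving per patient = (control repeats - CTCA repeats)/10 x repeat cost. Net saving = gross - 360 x (1 - m/10), where m is the number of the 10 controls who are scanned. The excess of gross over net is £360 for m = 0, £288 for m = 2, £180 for m = 5 and £0 for m = 10.

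- Equal repeats, m = 0: gross £0, net -£360.
- One fewer repeat in 10, m = 0: gross £693 to £1,000, net £333 to £640.
- The same with that one repeat control scanned (1 v 0 repeats, m = 1): the deduction is 360 x 0.9 = £324, so net £369 to £676.

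**Median, mean and range of 10 costs**, with £6,933 for the index and £10,000 per repeat, before any CTCA cost:

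| Repeats | Median | Mean | Range |
|---|---|---|---|
| 0 | £6,933 | £6,933 | £6,933 to £6,933 |
| 1 | £6,933 | £7,933 | £6,933 to £16,933 |
| 4 | £6,933 | £10,933 | £6,933 to £16,933 |
| 5 | £11,933 | £11,933 | £6,933 to £16,933 |

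The median averages the 5th and 6th ordered values, so it first moves at five repeats. The range shows that at least one repeat occurred, not how many.

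**Worked case: 4 control v 1 CTCA repeats, m = 0.** Medians: £6,933 v 6,933 + 360 = £7,293, so CTCA looks £360 dearer.

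- At £10,000 per repeat, means: 6,933 + 4,000 = £10,933 v 7,293 + 1,000 = £8,293; CTCA is lower by £2,640.
- At £6,933 per repeat, means: £9,706 v £7,986; CTCA is lower by £1,720.

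In this case a Mann-Whitney comparison also points towards CTCA being dearer: a control cost exceeds a CTCA-arm cost in 4 x 9 = 36 of 100 pairs. A t-test compares the means.

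**The same case under the practice the document describes.** The centre already scans patients after a failed attempt. If the four repeat controls are scanned and the CTCA-arm repeat is not rescanned, the control mean rises by 4 x 360/10 = £144. The net saving becomes £2,784 at £10,000 per repeat, or £1,864 at £6,933. The medians do not change.

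**How often an arm of 10 has 0 to 4 repeats.** The Existing knowledge section says "success rates increased from 68% to 79% between 2000 and 2011, and are as high as 90" per cent with high-volume operators, which implies failure rates of 32%, 21% and 10%. If every failure is repeated, the binomial probability of 0 to 4 repeats is 81.3%, 96.0% and 99.8% respectively. At assumed rates of 40% and 50% it is 63.3% and 37.7%. The document gives no local repeat rate, and the trial enrols only J-CTO scores of 2 or more, so the higher rates cannot be excluded.

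**Varying prices.** If index costs vary, the median does move somewhat. In an illustrative simulation (assumed: Poisson bed days with mean 0.5 at £855, normal variation with SD £300, £10,000 per repeat) it shifted on average by about £100 to £780 for 1 to 4 repeats, against £1,000 to £4,000 for the mean.

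**The case against.** The endpoint never claims to be a net saving. The rationale twice sets the £360 against the repeat cost, so the authors plainly have it in mind, and the separate comparison of financial cost could be the net analysis. The offset is a known price that any reader can subtract. Cost saved per patient is not observed in an individual; it is most naturally an arm-level difference divided by patients, which is a mean, so the median rule may never have been meant for it. The general rule also permits a t-test, which would reflect the repeats. Endpoint ii lets a reader rebuild part of the repeat cost, and endpoint iii a itself names readmission and further procedures.

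Most of this stands, and it limits the point to ambiguity in the wording. A reader might infer that the plan will leave the scan out; the document does not show that. A reader might take £0 to £360 as a strict bound; it is not, because it assumes one scan per CTCA-arm patient and further scans would move it. A reader might also infer that median and range together would usually differ between arms only by the price of the scan; that requires flat prices and no third procedure, and the document itself mentions third procedures and daily bed charges.

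What remains is that no component list says whether the CTCA is counted, nothing says that cost will be summarised by a mean, and nothing says which of the two tests applies to it. Endpoint ii counts patients with a second procedure, so it does not recover bed days or third procedures.

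**Conclusion.** The point holds as a minor one. Computed literally, endpoint iii a is a gross saving that exceeds the net saving by about £360 x (1 - share of controls scanned) per CTCA-arm patient. The practical consequence is greatest when repeats are equal: with no controls scanned, a net cost of £360 reads as £0. Where CTCA has fewer repeats, the sign is right at the document's prices and only the size is overstated.

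The median result is conditional on the general rule being applied to cost, and is exact only at flat unit prices. Under those conditions CTCA can look £360 dearer while its mean cost is £1,720 to £2,640 lower, or £1,864 to £2,784 lower if repeat controls are scanned after failure. With 10 per arm any cost result is descriptive, and the plan states no cost decision rule, so the trial's main conclusions are not affected.

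**What to change.** Define endpoint iii a as the difference between arms in mean total cost per randomised patient to 6 months. Total cost should count any CTCA performed in either arm, the index PCI, all repeat procedures, and readmission or bed days. Let the difference be negative, list the unit costs, show individual patient costs or the range beside the means, and label any interval as descriptive.

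The cost is a change of wording and a few extra data fields (CTCAs in either arm, repeat procedures, bed days). The reported figure will be less favourable to CTCA than a gross saving, unless every control is also scanned. A mean of 10 is sensitive to one expensive case, which is why the individual costs or range should accompany it. Sample size is unaffected.

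As a separate matter, the number of CTCAs should be reconciled. The Appendix total of £7,200 equals 20 x £360, whereas the comparator is no CTCA with 10 patients per arm, and the eligibility criteria require adequate CTCA images of every patient. The document does not settle which is intended, and the answer determines how much of the £360 is an incremental cost.

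### Secondary endpoint iii(d) is listed as a between-arm difference but can only occur after a CTCA review, so the no-CTCA count is fixed at zero and ordinary re-planning could be credited to CTCA

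*Combined protocol and SAP*

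**What the plan says.** In the Trial Protocol Synopsis, Outcomes row, secondary endpoint iii opens with "Procedural differences between the intervention CTCA arm versus no CTCA arm including", and its last item, (d), is "Change in CTO PCI strategy hierarchy as a result of the CTCA review". The matching secondary objective in the Objectives row is also a comparison of arms: "To assess if there are procedural differences between the intervention arm (CTCA) and usual care arm". The Intervention row gives CTCA before the procedure to the experimental group only; the conventional group goes to CTO PCI without it.

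The feasibility rationale says the study should "establish the role of a CTCA prior to CTO PCI to positively influence strategy and/or outcomes".

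The Sample size row sets 20 patients, 10 per arm, on grounds of what can be completed within a year. The analysis row states: "Categorical variables will be presented as percentage and compared with the chi square or Fisher's test". It gives no rule for choosing between the two tests and no significance level.

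The visible text does not define the strategy hierarchy, say when an initial strategy is recorded, or say who judges that it changed and why.

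**The concern.** A comparison of arms needs an outcome that can be observed in both. Item (d) names its own cause, a CTCA review, and that cause is assigned to one arm. The control count is therefore zero because of the definition, not because control operators keep to their first plan. An operator in the no-CTCA arm who looks again at the angiogram and reorders the approach has changed strategy, but the endpoint does not count it.

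In the CTCA arm the same second look happens with the CTCA to hand. Unless the plan was written down beforehand, separating what the CTCA changed from what would have changed anyway rests on the operator's own attribution. The documents describe no blinding, and an operator planning from a CTCA knows the arm.

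With 10 patients per arm, a planning measure is one of the more informative results this study could give. A high CTCA-arm figure set against a built-in zero could be taken as support for a larger trial when part of it is background re-planning.

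**Working it through.** **Inputs from the documents.** 10 patients per arm (2 × 10 = 20, which agrees with the stated total); chi-square or Fisher's test for categorical variables. There is no power calculation to reproduce, and no figure is given for (d).

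**Assumptions, not in the documents.** Two-sided significance level of 0.05; a rate *r* of re-planning without any CTCA influence, taken from 10% to 60%; no true CTCA effect; all re-planning in the CTCA arm counted as CTCA-related.

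**Step 1: p-values against a fixed 0/10.** With equal arms and x changes, all in the CTCA arm, two-sided Fisher p = 2 × C(10,x) / C(20,x).

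- x = 4: 2 × 210 / 4845 = 0.087
- x = 5: 2 × 252 / 15504 = 0.033

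So five or more changes are needed for Fisher p<0.05. The uncorrected chi-square for 4/10 v 0/10 is 20 × (4×10 − 6×0)² / (10 × 10 × 4 × 16) = 32000 / 6400 = 5.0, p = 0.025. Two of its expected counts are only 10 × 4 / 20 = 2, so Fisher is the appropriate test here.

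**Step 2: chance that re-planning alone gives p<0.05.** With control fixed at zero this is P(X ≥ 5) for X ~ Binomial(10, r), that is, the sum over k = 5 to 10 of C(10,k) r^k (1−r)^(10−k). The third column gives the same chance when change is measured identically in both arms at the same rate *r*, by summing over all pairs of counts for which Fisher p ≤ 0.05.

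| Assumed re-planning rate r | Control fixed at 0/10 | Both arms measured alike |
|---|---|---|
| 10% | 0.2% | 0.1% |
| 20% | 3.3% | 0.8% |
| 30% | 15.0% | 1.2% |
| 40% | 36.7% | 1.3% |
| 50% | 62.3% | 1.3% |
| 60% | 83.4% | 1.3% |

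**Step 3: bias in the estimate.** With control fixed at zero the expected apparent difference is r − 0 = r, although the true CTCA effect is nil. Measured alike it is r − r = 0. The overstatement is thus up to *r*, and it is present whether or not a test is run.

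**The case against.** The best reply is that (d) was never meant to be tested. Its list also holds CTCA radiation dose and CTCA contrast volume, which likewise exist in one arm only, and the analysis row does not name strategy change among its comparisons. This stands in part: no test of (d) is explicitly specified, and the p-values above are illustrations. But the text does not call (d) descriptive and places it under a between-arm heading. The parallel with CTCA dose is also incomplete: a control CTCA dose of zero is a true measurement, whereas control re-planning can happen and goes uncounted.

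Second, the definition already asks for attribution, so ordinary re-planning is formally outside it. That is right, and it is why the claim is that re-planning *could* be credited to CTCA. A reader might infer that it necessarily would be; the documents do not support that. The difficulty is that the visible text specifies no prior plan against which attribution could be checked.

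Third, the patient pathway and timeline figures are not shown and might contain a planning step. One may therefore not conclude that no baseline strategy is recorded, only that the visible text specifies none.

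Fourth, the zero follows from assignment and may not hold for every control patient. The feasibility rationale says "Current practice at our centre involves the use of CTCA in patients who have had an unsuccessful CTO PCI attempt" or previous CABG, and neither is an exclusion. The CTCA image criterion applies to all patients, and the Appendix costs CTCA at £7200 = 20 × £360. These points need reconciling in their own right. A few control patients with a usual-care CTCA would still not provide a measure of re-planning without CTCA.

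**Conclusion.** The point holds as a flaw in how (d) is defined and measured. As written, the between-arm contrast equals the CTCA-arm rate and contains no estimate of background re-planning.

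Its size depends on a rate that the documents do not give. At 10% to 20% the chance of a spurious p<0.05 stays under 5%; at 30% it is 15% and at 40% it is 37%, under the assumptions stated in the working. A reader might also infer that four changes out of ten would be enough to look significant. That relies on an uncorrected chi-square with expected counts of 2; by Fisher's test it takes five.

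The importance is moderate. Influence on strategy appears in one sentence of the rationale and is not among the listed objectives by name. This is one item of one secondary endpoint in a 20-patient feasibility study, and the primary endpoint is untouched. The change is still worth making before recruitment, because a baseline strategy that was not captured cannot be recovered later.

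**What to change.** 1. In the eCRF, record the operator's ranked strategy for all 20 patients before randomisation, and again immediately before PCI. The J-CTO score used for eligibility is angiographic, so the information for the first record should already exist.
2. Redefine (d) as any change between the two records, and compare the proportion changed between arms with Fisher's test.
3. Report changes that the operator attributes to CTCA separately, as a descriptive measure in the CTCA arm only.
4. Do not require an extra angiogram re-review in the no-CTCA arm. That would add a planning step to usual care and could alter the comparator for the primary endpoint; recording the plan twice does not need it.

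The cost is two short eCRF fields and a few minutes of operator time per patient. Writing the plan down may itself prompt slightly more planning in both arms. The operator remains unblinded at the second record, so the comparison is fairer but not free of that influence.
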